 - First, we will examine trends by 3 classes of MHT: ET (estrogen therapy), EPT (estrogen-progestin therapy) and tibolone. The time-series trend will be presented as the proportion of each class of MHT quarterly, calculated as the number of patients receiving each class of MHT divided by the total number of patients prescribed with MHT.
 - Second, we will examine trends by age group: all, 40-44, 45-49, 50-54, and 55-59. The time-series trend will be presented as the proportion of MHT use by each age group, calculated as the number of patients in each age group divided by the total number of patients prescribed with MHT.
 - Third, we will examine trends by menopausal symptoms: vasomotor symptoms, bone and joint symptoms, genitourinary symptoms, and psychosomatic symptoms. The time-series trend will be presented as the proportion of MHT use by each menopausal symptom, calculated as the

number of patients with each menopausal symptom divided by the total number of patients prescribed with MHT.

- Fourth, we will examine trends by the type of administration: systemic HT (oral), systemic HT (transdermal) and local HT (transvaginal). The type of administration of MHT will be classified as follows (Table 4). The time-series trend will be presented as the proportion of MHT use by each type of administration, calculated as the number of patients with MHT by each type of administration divided by the total number of patients prescribed with MHT.

Table 4. Type of administrations

Type of administrations	Ingredient code
Systemic HT (oral)	All ingredient codes except those for systemic HT (transdermal) and local HT (transvaginal)
Systemic HT (transdermal)	154902CCM 154904CPC 154905CPC 154906CPC 154907CSI 154908CCM 154908COM 154930CCM 154931CCM 154932CCM 154601CPC 154602CPC 154603CPC 154604CPC 154605CPC 154606CPC 335900CPC 336000CPC

Local HT (transvaginal)	155303CCM 155402CCM 155430CCM 155201CCM 155202CSP 507700CTB 336200CTB 155502CCM 219001CCS 219001CCM 219030CCM 336100CTB
-------------------------	--

4) Treatment regimens change of MHT across time

- We will depict treatment switch and discontinuation patterns across time by measuring the number of different treatments, including ET, EPT and tibolone, at time points of 3, 6, 9, and 12 months from the index date. Switching and discontinuation of MHT across time will be presented with a Sankey diagram.

5) Time to switch and discontinuation of MHT

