- Over time since the index date (initiation of MHT), Kaplan-Meier survival curves will be generated to calculate the time to non-persistence events including switch and discontinuation. Discontinuation will be defined as no subsequent prescriptions within 2 months of last prescription date.
- Switching MHT for any other treatment classes. (i.e. Switch will be defined as when a patient initiating a ET is prescribed a tibolone or EPT)

6) Treatment persistence and adherence

- Treatment persistence is calculated by the average length of treatment of the drugs prescribed at the index date. Persistence rate at 3-, 6-, 9-, and 12-month will also be calculated.

- Treatment adherence will be evaluated using medication possession ratio (MPR), calculated as the total number of days of medication supply divided by the number of days in the follow-up period.

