9.3.4 Sensitivity analyses

We will conduct sensitivity analyses as follows:

1. Discontinuation will be defined as no subsequent prescriptions within 4 months of last prescription date.
2. Treatment patterns of medication use for MHT by index treatment classes with patients for 2 years of follow-up.

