9.4. Data sources

Health Insurance Review and Assessment service (HIRA) database

This study will use the claims data of HIRA from January 1, 2011 to December 31, 2020. The National Health Insurance in South Korea covers approximately 98% of the entire Korean population. Under the terms of universal health coverage, all the claims data for reimbursement filed by healthcare providers are collected in HIRA database. This database contains a comprehensive information for healthcare services provided to beneficiaries such as diagnoses, treatment, procedures, surgical history, and prescription drugs. It includes an anonymized identifier, which represents the individuals in claims data, with age, sex, inpatient and outpatient diagnoses and drug prescriptions. The diagnoses are coded in compliance with KCD-8 which is a modified codes based on the International Classification of Disease, 10th revision (ICD-10). Information on prescribed drugs included generic name, prescription date, duration, and type of administration. Previous validation studies have been conducted to compare the diagnoses entered in the claims database with the actual diagnoses recorded in the patients' medical records from hospital or clinic chart review. The overall positive predictive value of the diagnoses in the South Korean healthcare database is 82%.

Korean Statistical Information Service (KOSIS)

The KOSIS was established by the Korean National Statistic Office in July 2007 under the national information strategy scheme. It is a statistical information system open to public that provides a

convenient access to wide variety of statistics. It currently provides more than 343 types of statistics produced by 120 organizations in South Korea. Moreover, KOSIS releases 100 major indicators of Korea, which provides information on health indicators and social status including mid-year population of each year and census population for each year.

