We will examine annual time-series trends in the prevalence of use for MHT by menopausal symptoms: vasomotor symptoms, bone and joint symptoms, genitourinary symptoms, and psychosomatic symptoms. The time-series trend will be presented as the proportion of MHT use by each menopausal symptom, calculated as the number of patients with each menopausal symptom divided by the total number of patients prescribed with MHT.

We will examine annual time-series trends in the prevalence of use for MHT by the type of administration: systemic HT (oral), systemic HT (transdermal) and local HT (transvaginal). The time-series trend will be presented as the proportion of MHT use by each type of administration, calculated as the number of patients with MHT by each type of administration divided by the total number of patients prescribed with MHT.

Switching and discontinuation of MHT for any other MTH type will be shown by using Kaplan-Meier curve. Discontinuation will be defined as no subsequent prescriptions within 2 months of last prescription date. We will conduct a sensitivity analysis where discontinuation of MHT is defined as a 4-month period without any MHT.

Treatment persistence is calculated by the average length of treatment of the drugs that were prescribed at the index date. Treatment adherence will be shown by calculating MPR (medication possession ratio), calculated as a total number of days of supply of medication divided by the number of days of the follow-up period.

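### Discontinuation is timed from the last prescription date and ignores days supplied, so on-time users of supplies longer than about two months count as stopped while still holding drug

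*Combined protocol and SAP*

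**What the plan says.** Section 9.3.2, item 5, states the use of the rule: "Kaplan-Meier survival curves will be generated to calculate the time to non-persistence events including switch and discontinuation". It then defines the event: "Discontinuation will be defined as no subsequent prescriptions within 2 months of last prescription date". The data analysis part of the Abstract (Section 4) and Section 9.7 give the same definition. None of the three mentions days supplied, end of supply or stock carried over from an early refill.

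Section 9.3.4 plans a sensitivity analysis with a longer window from the same starting point: "Discontinuation will be defined as no subsequent prescriptions within 4 months of last prescription date". Section 9.7 words that analysis differently: "We will conduct a sensitivity analysis where discontinuation of MHT is defined as a 4-month period without any MHT".

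Two other places show that supply information is available. Section 9.4 says of the claims data: "Information on prescribed drugs included generic name, prescription date, duration, and type of administration". Section 9.3.2, item 6, defines the medication possession ratio (MPR) as "calculated as the total number of days of medication supply divided by the number of days in the follow-up period".

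For the treatment-change outcome, Section 9.3.2, item 4, says "Switching and discontinuation of MHT across time will be presented with a Sankey diagram". It does not say which discontinuation rule applies there. Item 6 asks for persistence rates at 3, 6, 9 and 12 months, also without naming a rule.

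**The concern.** A gap rule is meant to detect a period without drug. This one measures the interval between prescription dates, so the tolerance after supply runs out shrinks as the prescription lengthens, and it turns negative once the supply exceeds the window. A woman on long prescriptions who never misses a day becomes an event, while a woman on 30-day prescriptions who refills four weeks late does not.

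The rule feeds objective 3. False events pull the discontinuation curve down. For the same woman over the same interval, the MPR would show complete supply while the Kaplan-Meier analysis showed her as stopped. If prescription length differs between estrogen therapy, estrogen-progestin therapy and tibolone, any comparison of the classes would partly reflect prescribing habits. The persistence rates and the Sankey diagram inherit the problem if they use the same rule.

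The event date is also missing. The on-time 90-day user could be given an event at day 0 (dated at her last prescription) or at about day 61 (dated at the end of the window).

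**Working it through.** **Inputs.** The windows of 2 and 4 months, both counted from the last prescription date, come from Sections 9.3.2, 9.7 and 9.3.4. The plan gives no figure for days supplied, S, so S is varied as an assumption. The plan also has no figure of its own to reproduce here.

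**Step 1: window length G in days.** Over every start date from 1 January 2012 to 31 December 2020:

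- 2 calendar months = 59 to 62 days (mean 60.9)
- 4 calendar months = 120 to 123 days (mean 121.7)

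**Step 2: time allowed after supply ends.** Grace = G − S. A negative value means the window closes while the woman still holds drug.

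| Days supplied, S | 2-month rule: 59 − S to 62 − S | 4-month rule: 120 − S to 123 − S |
|---|---|---|
| 30 | +29 to +32 | +90 to +93 |
| 60 | −1 to +2 | +60 to +63 |
| 90 | −31 to −28 | +30 to +33 |
| 180 | −121 to −118 | −60 to −57 |

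**Step 3: who is misclassified.** A woman who refills on the day her supply ends has an interval of S days between prescriptions, so she is an event when S > G. This is certain for S > 62 under the 2-month rule and for S > 123 under the 4-month rule. With a typical 61-day window and S = 90, the event falls at about day 61 with 90 − 61 = 29 days of drug in hand, before the 3-month persistence point. To avoid it she would have to refill 90 − 62 = 28 to 90 − 59 = 31 days early.

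**Step 4: does it depend on how "last" is read?** Suppose the word means only the final prescription in the data. A 90-day prescription dated 15 October 2020 has its window close on 15 December 2020, inside follow-up, which ends on 31 December 2020 (Section 9.2). Supply runs to 13 January 2021. The false event remains.

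**Step 5: gap counted from end of supply.** The on-time refiller then has a gap of 0 days for any S, so she is not an event under either window.

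**Step 6: illustration of size, both inputs assumed.** Let p be the share of women who refill on time with supplies over 62 days, and c their true 12-month continuation. If everyone else is classified correctly, the 12-month Kaplan-Meier estimate is too low by p × c:

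- p = 10%, c = 30%: 0.10 × 0.30 = 3 percentage points
- p = 40%, c = 70%: 0.40 × 0.70 = 28 percentage points

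This shows how the error scales. It is not an estimate for this cohort.

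**The case against.** The strongest reply is that the harm is conditional. The documents never mention a 90-day supply and give no distribution of prescription lengths. At 30 days there is no false event, and at 60 days the case is borderline. That stands: the defect in the rule is certain, but its overall size is not known. Nothing in the plan limits or checks prescription length, however, and even at 60 days or less the grace ranges from about 31 days to about 1.

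Second, the 4-month analysis clears the 90-day case, and a reader would see the two results differ. This is partly right. The primary curve is still uncorrected, the unequal grace remains, and on-time users of supplies over 123 days are still flagged. The Section 9.7 wording might already mean a gap in supply, but Section 9.3.4 says otherwise, so two analysts could program different analyses.

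Third, if events are dated at the end of the window, a woman who stops after one 30-day supply is dated about 31 days after her drug ran out, which lengthens measured time. This also stands. The false events act downward, but the net effect on a median depends on the missing event date and on the mix of supplies.

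Fourth, the plan does not say that the Kaplan-Meier curves are split by class, nor that the Sankey diagram and persistence rates use this rule. Those consequences are therefore stated only conditionally.

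**Conclusion.** The concern holds. Followed exactly, the rule counts an on-time refiller of any supply over 62 days as discontinued while she still holds drug; for a 90-day supply this is 28 to 31 days before it runs out. This follows from the text and the calendar alone. The planned sensitivity analysis reveals part of the problem but does not cure it. The size of the bias in this cohort cannot be derived from the documents; the 3 to 28 point range rests wholly on assumed inputs. The point should be fixed before analysis, because the rule defines a main event under objective 3 and the data for a sound rule are already required.

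**What to change.** Use one wording in the Abstract and Sections 9.3.2, 9.3.4 and 9.7, for example: *Discontinuation is the absence of a further MHT prescription within 2 months (sensitivity analysis: 4 months) after the end of supply of the latest prescription. End of supply is the prescription date plus days supplied, with overlap from early refills carried forward. The event is dated at the end of supply.* The team may prefer another gap length or event date, but should state and justify it. The text should also settle whether overlap carries across a switch of class, and whether the persistence rates and the Sankey diagram use the same rule. The two wordings of the 4-month analysis must be reconciled.

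No new data are needed. The cost is a sentence in four places, the short statements above and some programming. The team should also check how duration is recorded for transdermal and transvaginal products, which the documents do not describe.

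The change has a side effect that the plan should state: grace also lengthens for short supplies. For a 30-day supply it rises from about 31 to 61 days in the primary analysis and from about 92 to 122 in the sensitivity analysis, so persistence will read longer partly for that reason. One extra run with a 30-day gap after end of supply would roughly keep the present grace for 30-day supplies (61 − 30 = 31) and separate the two effects.

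### Any prescription from another MHT class counts as a switch and as non-persistence, even if the index class continues, so add-on use is miscoded in either direction

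*Combined protocol and SAP*

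**What the plan says.** Section 9.3.2, item 5, sets the time-to-event outcome: "Kaplan-Meier survival curves will be generated to calculate the time to non-persistence events including switch and discontinuation". The scope of a switch is "Switching MHT for any other treatment classes", and the operational wording is "Switch will be defined as when a patient initiating a ET is prescribed a tibolone or EPT". Section 9.7 repeats the outcome without adding a condition: "Switching and discontinuation of MHT for any other MTH type will be shown by using Kaplan-Meier curve".

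The class scheme has three levels: "First, we will examine trends by 3 classes of MHT: ET (estrogen therapy), EPT (estrogen-progestin therapy) and tibolone". Route of administration is separated in Table 4, but only for the administration trends and as a characteristic recorded on the index date.

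Two neighbouring outcomes depend on the same idea. Item 4 builds the Sankey diagram by "measuring the number of different treatments, including ET, EPT and tibolone, at time points of 3, 6, 9, and 12 months". Item 6 states: "Treatment persistence is calculated by the average length of treatment of the drugs prescribed at the index date".

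**The concern.** The event is the new prescription, and the rule does not ask whether the index class has stopped. That matters here because local vaginal estrogens share a class with systemic estrogens, and local treatment can be given alongside a systemic product. The likely reason for such a prescription lies within the study's own scope: atrophic vaginitis (N95.2) is an inclusion code in Table 1 and a genitourinary symptom code in Table 3.

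At stake is Objective 3, which covers treatment patterns, adherence and persistence. Women who carry on with their first treatment and add a second would appear in the item 5 curves as having left it. In the Sankey they could appear as flows between classes, which a reader would take as one therapy being abandoned for another.

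**Working it through.** The documents give no figure for switching or persistence, so there is none to reproduce. The check has three parts.

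**1. Does a vaginal product count as another class?** The transvaginal codes in Table 4, which begin "155303CCM 155402CCM 155430CCM 155201CCM 155202CSP", were matched to the ET block of Table 2.

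- Local codes by ingredient: conjugated estrogens 3, estriol 2, estriol/Lactobacillus 1, estradiol/Lactobacillus 1, estropipate 1, promestriene 4. Total 3 + 2 + 1 + 1 + 1 + 4 = 12.
- ET codes in Table 2, in the order listed there: 12 + 2 + 7 + 2 + 1 + 1 + 6 + 1 + 3 + 4 = 39.
- All 12 local codes are among the 39. None is in the EPT or tibolone block.

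**2. Is there a stop, overlap or add-on rule anywhere?**

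| Place | Content | Rule on concurrent classes |
|---|---|---|
| Abstract, data analysis | Sankey and Kaplan-Meier plans | none |
| Table 2 footnotes | estrogen and progestin monotherapies in the same prescription count as EPT | none for local estrogen added to a combined product or to tibolone |
| 9.3.2, item 4 | treatments counted at 3, 6, 9 and 12 months | none for a woman holding two classes |
| 9.3.2, item 5 | switch and discontinuation | none; the 2-month gap is not tied to the switch |
| 9.3.4 | 4-month gap; 2-year follow-up | switch rule not varied |
| 9.7 | repeats item 5 | none |

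Applied literally, the rule gives:

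- EPT or tibolone continued, vaginal estrogen added: switch to ET.
- Vaginal ET started and continued, EPT or tibolone added: switch from ET. This is the case the protocol spells out.
- Systemic ET continued, vaginal estrogen added: no event, because both are ET.

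**3. How large could the effect be?** Let S be true 12-month persistence on the index class. Let a be the proportion of those persistent women who have received another class by 12 months. Neither is in the documents, so both are assumed. The item 5 curve at 12 months then reads S × (1 − a).

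- S = 0.50, a = 0.05: 0.50 × 0.95 = 47.5%
- S = 0.50, a = 0.10: 0.50 × 0.90 = 45.0%
- S = 0.50, a = 0.20: 0.50 × 0.80 = 40.0%

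The understatement is S × a. For S from 0.30 to 0.70 and a from 0.02 to 0.20, it runs from 0.30 × 0.02 = 0.6 points to 0.70 × 0.20 = 14.0 points.

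**The case against.** The best defence is that switching ordinarily means replacement, that the worked example covers only women starting ET, and that this is a descriptive study in which the text is merely brief. Part of this stands: the example does not itself describe EPT or tibolone to ET, and that case rests on the general phrase about any other class. But the operational sentence makes the prescription the event and adds no condition. Two programmers working independently, as section 9.8 plans, could reasonably code it in different ways. Being descriptive does not help, since the definition produces the result.

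Four stronger readings are tempting, and the documents do not support them.

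- *The bias runs only against EPT and tibolone.* A vaginal-ET starter who adds EPT or tibolone is miscoded too. With no add-on rate in either direction, the net effect between classes is unknown.
- *The reported 12-month persistence rate will be too low.* Persistence rates at 3, 6, 9 and 12 months are listed under item 6, which follows the index drugs. The illustration applies to the item 5 curve only.
- *Items 5 and 6 contradict each other.* Item 6 does not say what ends treatment or whether a switch does. The two are unreconciled, which is a weaker statement.
- *The Sankey excludes a combined state.* Item 4 introduces its list of classes with a non-exhaustive word. A combined state is neither specified nor ruled out.

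**Conclusion.** The concern holds as a defect in a stated rule. Followed as written, item 5 records add-on use as a switch and as non-persistence whenever the added product belongs to another class. The item 5 curves then overstate switching and understate persistence. Item 4 has no stated rule for a woman holding two classes, and item 6 needs to be reconciled with item 5.

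The code overlap (12 of 12) and the absence of a stop or overlap rule are facts of the text. The size is not: the range of 0.6 to 14.0 points rests wholly on assumed values of S and a, and no direction of bias between classes can be claimed. The change should be made before the analysis is programmed, because neither planned sensitivity analysis would reveal the problem.

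**What to change.** In 9.3.2, item 5, and in 9.7:

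- Define a switch as a prescription of another class with no later index-class prescription within the discontinuation gap (2 months; 4 months in the sensitivity analysis), counted from the end of the index-class days of supply. Section 9.4 says the data hold prescription duration. Counting instead from the date of the new prescription would fail for longer supplies. For example, assuming a 90-day EPT supply, a cream on day 10 and an EPT refill on day 90, no EPT prescription falls in the 2 months after the cream although supply is unbroken.
- If the index class is refilled within that gap, code the event as add-on in either direction (local ET added to EPT or tibolone, or EPT or tibolone added to ET) and keep the woman persistent on the index class.
- Give the Sankey an add-on or concurrent state, and apply the same rule in items 4, 5 and 6. State in item 6 whether a switch ends treatment.
- The protocol counts the discontinuation gap from the last prescription date. Reconcile the two starting points, so that one woman is not add-on under one rule and discontinued under the other.
- Keep the any-prescription rule as a sensitivity analysis.

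The cost is a few sentences and one extra state in the program, with no new data. The downside is that a switch is confirmed only by looking forward, so switches close to 31 December 2020 cannot be confirmed and should be censored.

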9.2. Setting

The study cohort will include patients aged 40-59 years who were firstly diagnosed with menopausal symptoms and initiated MHT between January 1, 2012 and December 31, 2019. Patients with menopausal symptoms will be defined as at least one inpatient or outpatient claim with any of the following diagnosis codes (Table 1), restricted to primary and secondary diagnosis. The cohort entry date will be defined as the date of first diagnosis of menopausal symptoms and the index date will be defined as the date of the first prescription for MHT.

The exclusion assessment window will be defined as the year before the index date. Patients meeting any of the following criteria will be excluded: 1) patients diagnosed with breast cancer (C50, D05), endometrial cancer (C54.1), or granulosa cell tumor (C56); 2) patients diagnosed with coronary heart disease (I20-I25, I51.6), stroke (I60-64), or VTE (I80.2, I80.3 I26); 3) Patients diagnosed with viral hepatitis (B16-B19), cirrhosis (K70.2-K70.4, K71.7, K72.0-K72.1, K72.9, K74.0-K74.6, K76.1, K76.6-K76.7, R18, I85.0, I85.9, I86.4, I86.8, I98.2-I98.3), and hepatic cancer (C22); 4) patients diagnosed with gallbladder disease (K80, K81, K82, K83, K85.1), gallbladder cancer (C23), extrahepatic bile duct cancer (C24) within 1 year prior to the index date. Baseline characteristics including demographic characteristics, and medical institution type will be assessed on cohort entry date and comorbidities, concomitant medications and proxies of health status will be assessed within 1 year prior to cohort entry date. Menopausal symptoms will be assessed within 90 days after cohort entry date. Type of administration will be assessed on index date. (Figure 1).

PFIZER CONFIDENTIAL

In the identified study cohort, we will examine treatment patterns, adherence, and persistence of MHT during the follow-up window, which will be defined from the index date (date of first prescription for MHT) to the end of the study period (December 31, 2020).

[figure not shown]
[figure not shown]

Figure 1. Study design scheme

[§] Menopausal symptoms: Vasomotor symptoms, Bone and joint symptoms

Figure 2. Study Flowchart

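### Persistence is defined as an average treatment length with no censoring rule, no common horizon and no stated level for 'drugs', so a simple average runs short, most for late starters

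*Combined protocol and SAP*

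**What the plan says.** Section 9.2 takes women who "initiated MHT between January 1, 2012 and December 31, 2019" and follows them "from the index date (date of first prescription for MHT) to the end of the study period (December 31, 2020". Persistence belongs to Objective 3.

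Section 9.3.2, item 6 gives the measure: "Treatment persistence is calculated by the average length of treatment of the drugs prescribed at the index date". Section 9.7 repeats it almost word for word ("Treatment persistence is calculated by the average length of treatment of the drugs that were prescribed at the index date"), and so does the abstract. Item 6 adds fixed-time rates: "Persistence rate at 3-, 6-, 9-, and 12-month will also be calculated".

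Item 5 plans a time-to-event analysis alongside: "Kaplan-Meier survival curves will be generated to calculate the time to non-persistence events including switch and discontinuation". Switch is at class level ("Switching MHT for any other treatment classes", illustrated by a move from ET to tibolone or EPT). Discontinuation is a gap of 2 months after the last prescription, or 4 months in the sensitivity analysis of section 9.3.4.

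For the average, the plan gives no rule for treatment still running on 31 December 2020 and no horizon. It does not say whether 'drugs' means class, ingredient or product code.

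**The concern.** Every woman's data stop on the same calendar date, but start dates are spread over eight years. A long course begun in 2012 can be seen almost in full, while the same course begun in late 2019 is cut after about a year. An average that ignores this mixes how long women stay on treatment with when they started.

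Both simple ways of averaging have the problem. Counting ongoing users up to the cut-off treats them as if they stopped that day. Dropping them keeps mainly the short courses.

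If the average were later shown by class or by start year, groups with later uptake would look less persistent for a reason unrelated to behaviour.

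There is a smaller, separate gap. The average follows the index drugs, while the curve beside it follows the index class. If 'drugs' were read below class level, the two results would have different end points.

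**Working it through.** **Inputs from the documents.** Index dates run from 1 January 2012 to 31 December 2019, and data end on 31 December 2020 (section 9.2). Follow-up is thus 3,287 days for the first possible starter and 366 days for the last. The documents give no treatment length, discontinuation rate or persistence figure, so there is no plan figure to reproduce on this point. The only study-size figure, 4,293,747 in section 9.5, does equal the sum of the Table 7 year totals, but it plays no part here.

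**Assumptions.** Treatment length is exponential with true mean *m*; starts are spread evenly over 2012-2019; ongoing users are counted to the cut-off.

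**Formula.** With follow-up *T*, the expected observed length is *m*(1 − e^(−T/m)). Averaged over *T* uniform on (*a*, *b*) it is

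*m* − *m*²(e^(−a/m) − e^(−b/m)) / (*b* − *a*).

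With *m* = 2 years:

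- all starters (*a* = 1, *b* = 9): 2 − 4(0.6065 − 0.0111)/8 = 1.70 years
- 2012 starters (8, 9): 2 − 4(0.0183 − 0.0111)/1 = 1.97 years
- 2019 starters (1, 2): 2 − 4(0.6065 − 0.3679)/1 = 1.05 years, with 48% of them cut off

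The same calculation with exact calendar dates, in months:

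| True mean | Average, all starts | Shortfall, all | 2012 starters | 2019 starters | Shortfall, 2019 | Mean restricted to 12 months |
|---|---|---|---|---|---|---|
| 3 | 3.00 | 0.1% | 3.00 | 2.99 | 0.4% | 2.95 |
| 6 | 5.95 | 0.8% | 6.00 | 5.65 | 5.8% | 5.19 |
| 12 | 11.45 | 4.6% | 12.00 | 9.21 | 23% | 7.59 |
| 24 | 20.43 | 14.9% | 23.65 | 12.55 | 48% | 9.44 |
| 36 | 27.00 | 25.0% | 33.87 | 14.07 | 61% | 10.20 |

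**Other averaging rule.** With a true mean of 24 months, averaging completed courses only gives 1.88 years for 2012 starters and 0.67 for 2019 starters, further from the true 2 years than the first rule.

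**Other distribution.** A Weibull length with shape 0.6 and median 6 months (true mean 16.6) gives 15.45 months for 2012 starters and 8.20 for 2019 starters. The direction is the same.

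**Alternatives.** The restricted mean, *m*(1 − e^(−12/m)), is the same for every start year because all starters have at least 366 days. In a simulation of 400,000 women with a true mean of 24 months, the Kaplan-Meier median was 16.64 months (true 16.64) and the 12-month rate 0.606 (true 0.607), while the plain average was 20.4 months.

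**Level of 'drugs'.** Suppose the class-level mean is 12 months, a share *p* changes product code within class over 12 months, and that change ends treatment. The mean becomes 1/(1/12 + *h*) with *h* = −ln(1 − *p*)/12. For *p* = 10% it is 10.9 months, and for 20% it is 9.8. The 12-month rate falls from 0.368 to 0.331 and 0.294. These shares are assumptions; the documents give none.

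**The case against.** The best defence is that sound persistence measures are already planned. Every starter has at least 366 days, so the cut-off does not truncate the 3-, 6-, 9- and 12-month rates, and a Kaplan-Meier curve can handle censoring. That stands, and it confines the problem to one summary among several. It does not correct that summary, and no censoring rule is written for the curve either. The 2-year analysis in section 9.3.4 concerns treatment patterns by index class and does not name the average.

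It is also fair that the plan never says ongoing treatment is counted to the cut-off. That is inferred from silence; what can be shown is a missing rule.

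Two stronger readings are tempting:

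- *A class taken up late would look about half as persistent.* This needs a true mean near 2 years and a pure 2019-versus-2012 contrast. If one class's starts rise linearly from zero over 2012-2019 and another's fall linearly to zero, the apparent difference is 1.5% at a true mean of 6 months, 7% at 1 year, 17% at 2 years and about 23% at 3 years. The plan shows no class starting mostly in 2019 and does not say the average will be compared by class or start year.
- *Persistence would end at a change of strength.* Table 2 lists several codes for some ingredients but states no strengths, and the plan mostly works at class level (sections 9.3.1, 9.3.2 items 4 and 5, and 9.3.4). Only an undefined term is shown.

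**Conclusion.** The concern holds for the average treatment length. With a fixed data end and staggered starts, either simple averaging rule understates treatment length, and more so for later starters. That direction does not depend on the assumed distribution, but the size does. It is negligible overall if women typically stay 3 to 6 months (0.1% to 0.8%), modest at 12 months (4.6%) and substantial at 24 to 36 months (15% to 25%). These figures rest on an exponential length and even starts.

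A reader should not conclude that all the persistence results are compromised, or that this average is the leading result of Objective 3; the plan ranks none of its persistence measures. On the unit, the finding is limited to an undefined level for 'drugs' beside a class-level definition of switch.

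One edge case remains. A last prescription after about 31 October 2020 cannot be classified under the 2-month gap, nor one after about 31 August 2020 under the 4-month gap. This can touch the later time points for late-2019 starters.

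**What to change.** In section 9.3.2 (item 6), section 9.7 and the abstract:

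- Replace the average with the Kaplan-Meier median time on the index class and the mean time on treatment restricted to 12 months. Take both from the item 5 curve, with the event being the first of class switch or discontinuation.
- State that women still on treatment are censored at the end of data, and how last prescriptions too close to 31 December 2020 to apply the gap rule are handled, under both the 2-month and the 4-month definition.
- State that the drugs prescribed at the index date mean the index treatment class, to match item 5. Changes within class can be reported separately if wanted.

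The cost is a few sentences, with no new data and no new model, since the curve is already planned. The downside is small: a restricted mean is capped at its horizon and is less familiar than an average. Beyond 12 months the curve draws increasingly on earlier starters, so a median past that point assumes that persistence is similar across start years.
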